# 9.3.2 Analysis of the Primary Efficacy Endpoint(s)

A matched-pairs Wilcoxon signed rank test will be applied to the within-subject change in each outcome among subjects demonstrating full compliance with the exercise program. Additionally, weighted analysis of covariance (ANCOVA) will be used to test the change in each outcome adjusting for the measured level of compliance using data from all subjects. The values of each outcome at

CONFIDENTIAL

baseline and follow-up for all subjects will be the dependent variable and the ANCOVA model will include time (baseline versus follow-up) as the within-subject factor of interest covariates, the measure of compliance as numeric covariate and an anonymized subject ID as a classification factor so that the comparison of times will be based on their within-subject difference. The secondary objective is to assess the extent to which exercise induced improvements in DTI outcomes are can be at least partially explained by reduction in ROS will be addressed using linear regression, The baseline to follow-up change in each outcome will be the dependent variable and the model will include the measure of compliance as a numeric factor and the within-subject change in ROS as the numeric factor of interest. A second regression will be conducted with baseline factors (e.g., age, MNSI, general activity) added to the model in order to identify factors predictive of improvement in each outcome.

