# 2 Objectives and Purpose

# 2.1 Primary Objective

The primary objective is to assess and compare the interventions (exercise versus control phase) in terms of the baseline to follow-up change in the following outcomes: 1) DTI, plasma ROS level, and the MNSI assessment of DPN symptoms (Aim 1); and 2) leg mitochondrial function, oxidative capacity (31P-MRI), peak MV response (BOLD-MRI), the proportion of fat-free muscle (IDEAL-MRI) and leg muscle strength (Aim 2).

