# 9 Statistical Considerations

# 9.1 Statistical and Analytical Plans

The primary objective is to assess and compare the interventions (exercise versus control phase in the same individual) in terms of the baseline to follow-up change in the following outcomes: 1) DTI, plasma ROS level, and the MNSI assessment of DPN symptoms (Aim 1); and 2) leg mitochondrial function, oxidative capacity (31P-MRI), peak MV response (BOLD-MRI), the proportion of fat-free muscle (IDEAL-MRI) and leg muscle strength (Aim 2).

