# 9.3 Description of Statistical Methods

A weighted paired sample *t*-test will be used to assess whether each outcome changed from baseline to follow-up as a result of the exercise intervention. Weighted analysis of covariance (ANCOVA) will be used to compare the time points in terms of the change in each outcome. The change in each outcome from baseline to follow-up will be the dependent variable and the ANCOVA model will include the matching factors (age, baseline MNSI) and the measure of general activity level as numeric covariates and the binary indicator of intervention as a classification factor. The secondary objective is to assess the extent to which exercise induced improvements in DTI outcomes are mediated or explained by reduction in ROS. After testing the effect of the intervention on the change in DTI and the correlation between changes in DTI and ROS, an incomplete causal pathway meditational analysis will be conducted using the method of Baron and Kenny[63] with a bootstrap based test of the indirect (mediation) effect of ROS. The exploratory objective to identify baseline factors (e.g., age, MNSI, general activity) predictive of improvement, represented as the baseline to follow-up change in each outcome, will be addressed using linear regression and bivariate correlations. This analysis will be stratified by intervention and then conducted using data from both intervention groups combined. In each case, the assessment of compliance will be included as a weighting factor.

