## 9.3.1 General Approach

In this longitudinal, single-center study we will recruit 40 T2DM patients. Each participant will be imaged two times: upon enrollment (visit 1) and after completion of the 10 week exercise program (visit 3).

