### 9.3.4 Adherence and Retention Analyses

The analysis will follow the intention-to-treat (ITT) principle and include data from every subject irrespective of whether the subject was compliant with the assigned intervention. A quantitative assessment of compliance with the intervention, ranging from 0 (complete non-compliance) to 1 (full compliance), will be included as a weighting factor to allow more compliant subjects to contribute more to the analysis. The weight for the control phase will be set to 1 since subjects are not required to exercise.

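### The analysis headed primary (9.3.2) has no phase term, so it cannot give the exercise-versus-control-phase comparison that 2.1 and 9.1 make primary

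*Combined protocol and SAP*

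**What the plan says.** Section 2.1 sets the primary objective as to "compare the interventions (exercise versus control phase") on the change from baseline to follow-up. Section 9.1 repeats it and adds that the comparison is "exercise versus control phase in the same individual".

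Section 9.3.2, headed as the primary efficacy analysis, gives two tests. One is a Wilcoxon signed rank test of within-subject change in full compliers. The other is a weighted ANCOVA in all subjects, where "the ANCOVA model will include time (baseline versus follow-up) as the within-subject factor of interest"; its other terms are compliance and subject ID.

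Section 9.3 describes a different ANCOVA, on change scores with a binary intervention indicator, which "will be used to compare the time points in terms of the change in each outcome". There "the ANCOVA model will include the matching factors (age, baseline MNSI"), and the exploratory analysis is "conducted using data from both intervention groups combined". Section 9.3.4 adds: "The weight for the control phase will be set to 1 since subjects are not required to exercise".

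On imaging, section 9.3.1 states: "Each participant will be imaged two times: upon enrollment (visit 1) and after completion of the 10 week exercise program (visit 3"). Section 12.3 also counts two scans. Sections 1.2 and 3.1 give three, and Attachment A puts them at Weeks 1, 5 and 18.

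**The concern.** A two-level time factor estimates one change. The objective asks for the difference between two changes, one per phase. No reading of baseline turns the first into the second.

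- If baseline is the enrolment scan, as 9.3.1 implies, any change during the 4-week non-exercise phase is counted as an exercise effect, and the Week 5 scan goes unused.
- If baseline is the pre-exercise scan, as 6.4.4 suggests, that carry-in disappears, but the control phase still plays no part in the test.

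An analyst who follows 9.3.2 therefore reports an uncontrolled pre-post change under an objective that promises a control-phase comparison. One who follows 9.3 may report something else from the same data. Section 9.4 claims power for the phase difference, which the section headed primary does not test. If only two scans are taken, no control-phase change exists for any MRI outcome.

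**Working it through.** **Inputs.** From Table 4 in 9.4, mean (SD) of within-subject change: BOLD exercise 1.11 (1.26), control 0.18 (1.42); PCr exercise 10.61 (12.85), control 0.06 (8.53); MNSI exercise 1.20 (1.78), control not given. Baseline means from Table 3: 3.24, 41.16 and 5.2. n = 40, two-sided 5% (9.4). Call the scans at Weeks 1, 5 and 18 V1, V2 and V3.

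**1. The plan's within-phase power.** The change detectable with 80% power (one-sample noncentral t, n = 40) is 0.572 for BOLD, 5.84 for PCr and 0.809 for MNSI. Divided by the baseline means, these are 17.7%, 14.2% and 15.5%, inside the stated 10% to 18%. This claim reproduces, but it concerns change within one phase.

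**2. The plan's phase-difference figures.** BOLD: (1.11 - 0.18)/0.18 = 5.17, printed as 5.2%. PCr: (10.61 - 0.06)/0.06 = 175.8, printed as 176%. So 9.4 does address exercise minus control, expressed as a multiple of the control change. The printed minimum detectable values, 4.5 and 120, come out at 4.7 and 115 with two independent groups of 40, or 4.8 and 117 with paired changes at correlation 0. The exact method cannot be identified. Power is 86% (BOLD) and 99% (PCr) either way.

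**3. What each analysis estimates.** For illustration, assume the Table 4 control change applies to the 4-week phase; the readable text gives neither its duration nor its sample size.

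| Estimate | BOLD | PCr |
|---|---|---|
| 9.3.2 with baseline V1: V3-V1 | 1.11 + 0.18 = 1.29 | 10.67 |
| 9.3.2 with baseline V2: V3-V2 | 1.11 | 10.61 |
| Objective: (V3-V2)-(V2-V1) | 1.11 - 0.18 = 0.93 | 10.55 |

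For BOLD, 1.29/1.11 = 1.16 and 1.29/0.93 = 1.39. For PCr the gaps are about 1% or less. The BOLD control change is itself not distinguishable from zero: 0.18/(1.42/√40) gives t = 0.80, 95% CI -0.27 to 0.63 at n = 40.

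**4. BOLD rejection rates with no exercise effect** (noncentral t, noncentrality = mean × √40/SD). Steady drift is 0.18/4 = 0.045 per week: 17 weeks give 0.765, 13 weeks give 0.585, and the contrast is 0.585 - 0.18 = 0.405.

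| Test | 0.18 is a one-off | 0.18 continues at the weekly rate |
|---|---|---|
| V3-V1 (SD 1.42 to 1.26) | 12-14% | 91-96% |
| V3-V2 (SD 1.26) | 5% | 82% |
| Phase contrast (r = -0.5 to 0) | 8-9% | 19-26% |

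For PCr every entry is 5.0-5.4%. Neither V3-V2 nor the phase contrast is better in both cases.

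**5. Power of the within-person contrast.** SD = √(s₁² + s₂² - 2·r·s₁·s₂), where r is the correlation between the two phase changes. The documents do not give r. If the phases share V2, compound symmetry with equal SDs gives r = -0.5.

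| r | BOLD SD | BOLD SE | BOLD power | PCr power |
|---|---|---|---|---|
| +0.5 | 1.347 | 0.213 | 99% | >99% |
| 0 | 1.898 | 0.300 | 86% | 99% |
| -0.25 | 2.121 | 0.335 | 77% | 97% |
| -0.5 | 2.322 | 0.367 | 70% | 94% |

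Section 9.4 assumes a visit-to-visit correlation ρ of 0.5. Keeping r = -0.5 and scaling the SDs by √((1-ρ)/0.5), BOLD power reaches 80% at ρ of about 0.61 and 89% at 0.70. The 70% is therefore a low case.

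**6. Are the control-phase values measured?** Section 3.2.1 places MNSI and ROS before and after the 10-week intervention. ROS comes from the time-0 blood of the OGTT, which 6.2.1 describes as pre- and post-intervention. Attachment A has OGTT and bloodwork at Weeks 1 and 18, and MNSI at Weeks 0, 1 and 18. Calf performance is in exercise weeks 1 and 10 only (Table 2). None of these shows a value at both ends of the non-exercise phase.

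**The case against.** The strongest reply is that the plan is inconsistent rather than missing a comparison. Section 9.3 has an intervention indicator, 9.3.4 weights the control phase, and 9.3.6 refers to both phases. That is correct, and the point here is not that the plan lacks a phase comparison. But no text ranks 9.3 above the section headed primary, and the 9.3 model speaks of matching and groups in a single cohort and names no subject term for two changes per person.

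Second, the objective may be the leftover text. The hypotheses in 9.2 name no control phase, 9.3.5 rules out group comparison, and participation is given as about 10 weeks in the Protocol Summary and at least 10 in 4.5. Rewording the objective is thus a legitimate repair. Still, 9.3.5 excludes groups, not phases, and 3.1 describes the 4-week non-exercise period.

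Third, the contents list and 4.7.2 name a post-non-exercise visit (6.4.3) whose text is not readable here. It could list the missing measurements, and Attachment A is declared to be outside the protocol. This stands, and it makes the ROS, MNSI and strength point conditional.

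Fourth, the drift figures extend a noise-level 0.18, and the power range depends on an assumed correlation. Both stand: they illustrate and do not estimate. The mismatch between objective and primary analysis does not rest on them.

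**Conclusion.** The concern holds and must be fixed: the section headed primary does not test the primary objective under either reading of baseline. That conclusion follows from the text alone.

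The size of any bias is unknown. If the Table 4 control change applied to this 4-week phase and baseline were V1, the BOLD estimate would be 16% above V3-V2 and 39% above the phase difference; PCr would hardly change. The claim of more than 80% power for the exercise-control difference is secure for PCr (at least 94% over the range shown). For BOLD it depends on an unstated correlation. The gap for ROS, MNSI and leg strength rests on the readable schedule.

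**What to change.** 1. Reconcile the scan count in 9.3.1 and 12.3 with 1.2, 3.1 and Attachment A, and state which scan is baseline in 9.3.2.
2. If three scans are confirmed, make one analysis primary for the MRI outcomes that contains phase, uses all three visits and treats subject as the repeated unit. Visit as a three-level factor would serve. So would the 9.3 change-score model with its indicator relabelled as phase and within-subject correlation included. Report the difference between phase changes together with V3-V2 and its confidence interval. State that the scans are about 4 and 13 weeks apart, and that the contrast over-corrects if the control-phase change is a one-off. If only two scans are taken, reword the objective as an uncontrolled pre-post change.
3. Replace the matching and group wording in 9.3 with phase wording.
4. Unless measurement at both ends of the non-exercise phase is confirmed, report plasma ROS, MNSI and leg strength as uncontrolled pre-post changes.
5. Restate the exercise-control power in 9.4 for the within-person contrast, with the assumed correlation and its range.

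**Cost.** Wording only for the MRI outcomes, if the Week 5 scan is confirmed. The phase contrast is less precise: BOLD standard error 0.30 to 0.37 (r = 0 to -0.5) against 1.26/√40 = 0.20 for V3-V2, so the restated BOLD power may be lower. ROS, MNSI and leg strength lose the controlled claim unless the extra measurements are confirmed.

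### In the section 9.3.2 weighted ANCOVA, compliance is aliased with subject ID, so the covariate does not adjust the test of change for compliance

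*Combined protocol and SAP*

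**What the plan says.** Section 9.3.2 first applies a Wilcoxon signed rank test to fully compliant subjects. It then states that "weighted analysis of covariance (ANCOVA) will be used to test the change in each outcome adjusting for the measured level of compliance", using all subjects. The dependent variable is the outcome value at each of the two times. The terms are "time (baseline versus follow-up) as the within-subject factor of interest covariates", and "the measure of compliance as numeric covariate and an anonymized subject ID as a classification factor". The subject factor is there "so that the comparison of times will be based on their within-subject difference". No time-by-compliance term is listed.

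Section 9.3.4 says: "A quantitative assessment of compliance with the intervention, ranging from 0 (complete non-compliance) to 1 (full compliance), will be included as a weighting factor". It sets the control-phase weight to 1, but says this of the weight only. Section 9.3.1 gives two imaging times per participant, at enrolment and after the exercise programme.

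Later in section 9.3.2, a separate regression takes each person's change as the dependent variable, with compliance and the change in ROS as predictors.

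**The concern.** An ANCOVA with a subject factor compares each person with himself or herself. Anything constant within a person drops out of that comparison, and a single compliance score for the exercise programme is constant within a person. The covariate meant to deliver the adjustment would then have no effect on the estimate it is meant to adjust.

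What is at stake is what the result means. Because the Wilcoxon test is limited to full compliers, this ANCOVA is the only test of change in section 9.3.2 that uses everyone, and it applies to every outcome. A report that follows the plan would call its time effect compliance-adjusted when the covariate has adjusted nothing.

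**Working it through.** **The plan's own figures.** Section 9.4 gives no figure for this model. Its power statement is for the mean within-subject change with n = 40 and two-sided 5%. Using the Table 4 exercise SDs and the Table 3 baseline means, the detectable change at 80% power is, for BOLD, (1.960 + 0.842) × 1.26/√40 = 0.558, or 17.2% of 3.24. For PCr and MNSI it is 13.8% and 15.2%. With the noncentral t the three are 17.7%, 14.2% and 15.5%, so the stated upper end of 18% reproduces. Power at the expected changes of 34.3%, 25.8% and 23.1% is 99.97%, 99.9% and 98.6%, so the claim of more than 80% also reproduces. None of this bears on the aliasing.

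**Inputs.** There are 40 subjects (section 9.4), two rows each (sections 9.3.1 and 9.3.2), and one compliance score c_i per subject (the natural reading of section 9.3.4).

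**Rank.** Let D_i be the indicator column for subject i. The compliance column is C = Σ c_i D_i, an exact linear combination of the ID columns.

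| Model | Columns | Rank | Residual df |
|---|---|---|---|
| time + ID | 41 | 41 | 80 − 41 = 39 |
| time + ID + compliance | 42 | 41 | 39 |

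Weighting multiplies each row by a constant, which leaves the dependence intact. The 39 degrees of freedom assume that no weight is exactly zero. A third imaging time, as sections 1.2 and 3.1 describe, would raise the counts but not remove the dependence.

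**The same result from the differences.** With time effect b and compliance coefficient g, each person's change is d_i = b + g(c_i − c_i) + error = b + error. Compliance cancels.

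**Numerical check.** Outcomes and compliance were simulated, so the values only illustrate the result; the rank argument does not depend on them.

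| Weights (baseline row, follow-up row) | Time estimate (SE) without compliance | With compliance |
|---|---|---|
| 1, 1 | 8.033 (1.643) | 8.033 (1.643) |
| c, c | 8.027 (1.663) | 8.027 (1.663) |
| 1, c | 7.992 (1.653) | 7.992 (1.653) |

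Over 1,000 random data sets with the 1, c weights, the largest difference in estimate or SE was about 3 × 10⁻¹⁴, which is rounding error. With a random subject effect and complete data the compliance coefficient becomes estimable, but the time estimate is again 8.033 in both fits.

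**What the weights do.** With row weights w1 and w2, subject i's change gets weight w1·w2/(w1 + w2). That is proportional to c for weights c, c, and equals c/(1 + c) for weights 1, c. Suppose 20 people have c = 1 and change 10.61, and 20 have c = 0.25 and change 0:
- unweighted: 10.61 × 0.5 = 5.3
- weights c, c: 10.61 × 1/(1 + 0.25) = 8.5
- weights 1, c: 10.61 × 0.5/(0.5 + 0.2) = 7.6

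The weights move the estimate toward compliant people. They do not hold compliance fixed.

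**An estimable form.** Adding time × (c − mean c) raises the rank to 42 and leaves 80 − 42 = 38 residual degrees of freedom. In the unweighted simulated data the time estimate stays at 8.033 and the SE goes from 1.643 to 1.664. In the weighted fits, centring at the plain mean shifts the time estimate (8.027 to 7.892 with weights c, c; 7.992 to 7.934 with weights 1, c). The centring mean must therefore use the same weights as the model.

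**The case against.** The strongest reply is that a redundant term does no harm. Least-squares software drops the column or uses a generalised inverse, and the time effect comes out the same. That stands: the term causes no bias, no Type I error inflation and no loss of degrees of freedom. What it does not answer is that the section states a purpose which the term cannot serve.

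A reader might infer that compliance has no influence on this analysis at all. The documents do not support that, because the ANCOVA is weighted by compliance and the weights do move the estimate. Only the covariate is inert.

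A reader might also infer that the same data would give several conflicting time effects, even of opposite sign, according to how the baseline row is coded. If compliance were coded k at baseline and c_i at follow-up, then d_i = b + g(c_i − k), and b would be the change at full compliance for k = 1 or at zero compliance for k = 0. But the plan states no such coding; the value of 1 in section 9.3.4 concerns the weight. Recoding would be an analyst's choice, and how far the results differed would depend on compliance data that the documents do not give.

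Finally, section 9.3.2 already has a regression in which compliance is estimable. It also contains the change in ROS, so its compliance slope is conditional on a proposed mechanism. It covers part of the ground, but it does not make the ANCOVA a compliance-adjusted test.

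**Conclusion.** The concern holds for the covariate term. If compliance is one score per person, it is exactly aliased with subject ID under any weighting, and the stated adjustment is not delivered by that term. The effect of the term on the time estimate and its SE is zero. The time test remains valid as a test of within-person mean change, weighted by compliance if the weights are kept. The fault lies in what the model is said to do, and it affects the section's only all-subject test of change, for every outcome.

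The conclusion rests on two readings: one compliance value per person, which section 9.3.4 implies but does not say outright, and subject ID as a fixed classification factor, as section 9.3.2 says. A random subject effect would leave the time estimate unchanged with complete data. Row-level coding would make compliance estimable, but it would change what the time effect means. The Wilcoxon test and the regression with ROS change are not affected.

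**What to change.** - Remove the compliance main effect from the subject-ID model, together with the statement that this model adjusts for compliance.
- Describe its time effect as the within-person mean change, or as a compliance-weighted mean change if the weights are kept. Report the unweighted mean change as the all-subject (ITT) estimate.
- If compliance is wanted as a covariate, add time × (compliance minus its mean), using the mean that matches the model's weighting. Equivalently, regress each person's change on centred compliance, with the corresponding weights and without ROS change. Report the slope with its confidence interval, and the predicted change at full compliance as supplementary.
- If row-level coding was intended, state the baseline-row value and what the time effect then estimates.

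The cost is revised analysis-plan wording, one extra regression per outcome, and one residual degree of freedom in that regression (39 to 38). No new data or patients are needed, and the required sample size does not change materially.

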# 2.3 Exploratory Objective (if applicable)

The exploratory objective is to identify baseline factors (e.g., age, MNSI, general activity) predictive of improvement, represented as the baseline to follow-up change in each outcome. This objective will be addressed using linear regression and bivariate correlations.

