### 9.3.6 Exploratory Analyses

The exploratory objective to identify baseline factors (e.g., age, MNSI, general activity) predictive of improvement, represented as the baseline to follow-up change in each outcome, will be addressed using linear regression and bivariate correlations. This analysis will be stratified by intervention and then conducted using data from both phases combined. In each case, the assessment of compliance will be included as a weighting factor

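### Section 9.3.2 looks for baseline predictors of improvement in a model that already contains change in ROS and compliance, and Sections 2.3, 9.3 and 9.3.6 specify the same objective differently

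*Combined protocol and SAP*

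**What the plan says.** Section 2.3 sets the aim: "The exploratory objective is to identify baseline factors (e.g., age, MNSI, general activity) predictive of improvement". It names the method in the next sentence: "This objective will be addressed using linear regression and bivariate correlations".

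Section 9.3.2 approaches the same aim from another direction. It begins with a regression for the question whether a fall in ROS explains the DTI improvements: "The baseline to follow-up change in each outcome will be the dependent variable and the model will include the measure of compliance". That model is completed as follows: "the model will include the measure of compliance as a numeric factor and the within-subject change in ROS as the numeric factor of interest". The next sentence turns to baseline predictors of improvement: "A second regression will be conducted with baseline factors (e.g., age, MNSI, general activity) added to the model in order to identify factors predictive". The natural antecedent of the model is the regression just described, so compliance and ROS change stay in it.

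Section 9.3.6, the section devoted to exploratory analyses, says that the objective "will be addressed using linear regression and bivariate correlations" and adds: "In each case, the assessment of compliance will be included as a weighting factor". Section 9.3 carries essentially the same text. Neither attaches a ROS-change term to this objective, and in both compliance is a weight, not a covariate.

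Section 9.1 lists plasma ROS itself among the outcomes: "DTI, plasma ROS level, and the MNSI assessment of DPN symptoms (Aim 1".

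**The concern.** A baseline predictor of improvement is something known at enrolment that is associated with the later change. The second regression in Section 9.3.2 estimates a different quantity: the association of the factor with outcome change among subjects with the same ROS change and the same compliance. Both of those are realised after baseline, and both may depend on the baseline factors. Section 9.3 treats ROS reduction as a possible mediator of the exercise effect on DTI. Compliance is a plausible route by which age, neuropathy severity or habitual activity could influence benefit.

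Two distortions are possible. Whatever part of a factor's association runs through ROS change or compliance is removed from its coefficient. And if something unmeasured drives both ROS change (or compliance) and the outcome, holding the post-baseline variable fixed can induce an association for a factor that has none.

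There is also a conflict of specification. One analyst could follow Section 9.3.2 and another Section 9.3.6, report different predictors, and both claim to have followed the plan.

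**Working it through.** **The plan's own figures.** No figure in the plan concerns this regression. The power statement in Section 9.4 (80% power for changes of 10% to 18% of the baseline mean) is about mean within-subject change. With the exercise SDs in Table 4, n=40 and the exact t calculation, the detectable changes are 0.572/3.24 = 17.7% (BOLD), 5.837/41.16 = 14.2% (PCr) and 0.809/5.2 = 15.5% (MNSI), all inside the stated range. Only n=40 and the two-sided 5% level carry over to what follows.

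**The specifications side by side.**

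| Section | Change in ROS | Compliance |
|---|---|---|
| 9.3.2, second regression | covariate | numeric covariate |
| 2.3 | not named | not named |
| 9.3, exploratory sentences | not named | weight |
| 9.3.6 | not named | weight |

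**Loss of a true predictor.** Let X be the baseline factor, R the change in ROS and Y the outcome change, all standardised. Let a be the path from X to R, b the path from R to Y, and d the direct path from X to Y. The slope of Y on X alone is d + ab; with R in the model it is d. Assume a total effect of 0.5 and a = 0.6, with a share s of the effect running through R, so that d = 0.5(1 − s). Results from 8,000 simulated trials of 40 per row, with compliance simulated as unrelated noise so that only the ROS term acts:

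| Share through ROS change | Slope, X alone | Detected | Slope, 9.3.2 model | Detected |
|---|---|---|---|---|
| 0% | 0.50 | 92% | 0.50 | 77% |
| 25% | 0.50 | 92% | 0.37 | 54% |
| 50% | 0.50 | 92% | 0.25 | 32% |
| 75% | 0.50 | 92% | 0.13 | 14% |
| 100% | 0.50 | 92% | 0.00 | 5% |

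In the first row the slope is intact but precision is lost. Adding a covariate correlated 0.6 with X multiplies the variance by 1/(1 − 0.36) = 1.56, and so the standard error by 1.25.

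Compliance can act in the same way. With assumed paths of −0.5 (factor to compliance) and 0.5 (compliance to outcome), the total slope is −0.5 × 0.5 = −0.25. It is detected about 35% of the time without adjustment. With compliance in the model the slope is 0.00, detected 5% of the time.

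**A null factor flagged as predictive.** Let X have no effect on Y, and let an unmeasured U act on both R and Y with strength u. The slope of Y on X alone is 0; with R in the model it is −a·u²/(1 − a²). For a = 0.3, u = 0.5 this is −0.3 × 0.25/0.91 = −0.082 (simulated −0.083). For a = 0.5, u = 0.7 it is −0.5 × 0.49/0.75 = −0.327 (simulated −0.327). Share of trials with p<0.05 in the 9.3.2 model:

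| Factor to ROS change (a) | u = 0 | u = 0.3 | u = 0.5 | u = 0.7 |
|---|---|---|---|---|
| 0 | 5% | 5% | 5% | 5% |
| 0.3 | 5% | 5% | 8% | 20% |
| 0.5 | 5% | 6% | 15% | 53% |
| 0.6 | 5% | 7% | 21% | 77% |

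With X alone the rate is about 5% in every cell.

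**ROS as its own regressor.** Taken literally, the dependent variable in Section 9.3.2 is the change in every outcome, and ROS is an outcome. Regressing ROS change on ROS change gives a coefficient of 1, no residual, and 0 for every baseline factor.

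**The case against.** The strongest reply is that Section 9.3.6 is the dedicated section and does not contain the fault. Its correlations, like those in Sections 2.3 and 9.3, do not hold ROS change or compliance fixed as covariates, so a factor hidden by the 9.3.2 model could still show there. This stands as a limit on the point. A reader might infer that the plan will erase real predictors and create false ones; the documents do not support that, because the 9.3.2 regression is not the only one planned. It does not remove the point: Section 9.3.2 is the one place that builds the predictor regression from an explicit covariate list, and no section is given precedence.

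The distortions are also conditional. A coefficient vanishes only under complete mediation. A null factor is flagged too often only if it affects a conditioned variable that also shares an unmeasured cause with the outcome. Weak paths do almost nothing. This too stands, and the sizes are therefore shown as a range.

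The sample is small in any case. In the compliance example, even the unadjusted model misses the factor about 65% of the time. That is true, but it gives no reason to ask the wrong question of the data.

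On the self-regression, it can be said that the ROS model is introduced for DTI, so the outcomes meant may be the DTI ones only. That reading is possible. The predictor regression would then cover fewer outcomes than Section 2.3 intends.

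Finally, a reader might infer harm to patient selection. The plan states only that it wants to identify predictive factors and proposes no such use.

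**Conclusion.** The point holds as a mismatch between model and objective, together with an unresolved conflict between sections. As written, the second regression in Section 9.3.2 yields associations net of two post-baseline variables, one of them the plan's hypothesised mediator for DTI. That is not the predictive value sought in Section 2.3.

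Its size cannot be fixed from the documents, which give no path strengths. Under the assumed paths at n=40, the effect on a true predictor runs from a loss of precision alone to complete disappearance. For a null factor, false positives are about 5% to 8% with weak to moderate paths (0.3, with a common cause of 0.3 to 0.5). They rise to about 50% with strong paths (0.5 and 0.7), and higher only at the extreme corner of the grid.

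It does not follow that weighting by compliance has been shown to bias the predictor analysis. The calculations contain no weighted scenario; they show only what the two covariates do. The weight is nevertheless post-baseline, which is reason enough to show the unweighted result as well. The analysis is exploratory, and no primary test, power figure or sample size depends on it.

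**What to change.** - In Section 9.3.2, delete the sentence that adds baseline factors to the ROS-change model.
- Make Section 9.3.6 the single specification for baseline predictors, and have Sections 2.3 and 9.3 refer to it. The regressors should be baseline variables only, with neither ROS change nor compliance as a covariate.
- In Section 9.3.6, report an unweighted version alongside the compliance-weighted one.
- Keep the ROS-change regression in Section 9.3.2 for the mediation question, and state that ROS is not a dependent variable there.

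The cost is wording in the statistical sections and one additional unweighted fit per outcome. No data collection, procedure or sample size changes.
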